#### Duration of Intracranial, Extracranial, and Overall Response in Cohorts A, B, C, and D

Duration of intracranial, extracranial, and overall response will be summarized separately for subjects with a confirmed of intracranial, extracranial, or overall CR or PR and is defined as the time (in months) from the initial response (CR/PR) to first documented disease progression or death due to any cause. This will be based on responses from the investigator assessment. Censoring rules will follow those of the primary PFS analysis defined in Section 11.1.

If sample size permits, the median duration of response will be calculated from the Kaplan-Meier estimates. First and third quartiles will also be calculated along with associated 95% confidence intervals if there are a sufficient number of responders who subsequently progress or die due to any cause.

Figures and listings of duration of response will also be provided.

The duration of intracranial, extracranial, and overall response per independent reviewer-assessment will also be summarized. Figures and listings of duration of independent reviewer-assessed response will also be provided.

#### Progression-Free Survival in Cohorts A, B, C, and D

Progression-Free survival (PFS) is defined as the interval of time (in months) between the date of first dose of study treatment and the earliest of the date of overall disease progression and the date of death due to any cause. Disease progression will be based on assessments by the investigator.

The date of documented disease progression will be defined as the date of overall disease progression based on imaging data. The date of death will be taken from the Record of Death page. Death on study due to any cause will be used.

Subjects who progressed or died after an extended period without adequate intracranial and extracranial assessment will be censored at their date of last adequate intracranial and extracranial assessment prior to progression or death even if subsequent information is available regarding intracranial or extracranial progression or death. An adequate assessment is defined as an assessment where the investigator-determined response is CR, PR, or SD. The date of response at that assessment will be used for censoring. Because the assessment schedule changes during study treatment, specific rules for identifying extended loss to follow-up or extended time without an adequate assessment are provided in Section 9.

If anti-cancer therapy is started without documented overall disease progression or is started prior to documented overall disease progression, then PFS will be censored at the date of the last adequate assessment that is on or before the date of initiation of anti-cancer therapy (i.e., if an assessment occurs on the same day as the start of new anti-cancer therapy the assessment will be used). The date of response at the last adequate assessment will be used as the censoring value.

If a subject has only a baseline visit or does not have an adequate assessment that is on or before the date of initiation of anti-cancer therapy, PFS will be censored at the date of first dose of study treatment.

If a subject has neither progressed nor died nor started new anti-cancer therapy, then PFS will be censored at the date of the last adequate assessment defined as an assessment where the investigator-assessed response is CR, PR, SD. The date of response will be used as the censoring date.

A summary of the assignments for progression and censoring dates for PFS are specified in Table 2.

**Table 2 Assignments for Progression and Censoring Dates for PFS Analysis**

Situation	Date of Event (Progression/Death) or Censoring	Outcome Event (Progression/Death) Or Censored
No ( or inadequate ) baseline intracranial and extracranial tumor assessments and the subject has not died	First dose of study treatment	Censored

Situation	Date of Event (Progression/Death) or Censoring	Outcome Event (Progression/Death) Or Censored
No post-baseline intracranial or extracranial assessments and the subject has not died	First dose of study treatment	Censored
Progression documented between scheduled visits	Date of assessment of earliest source of progression 	Event
No progression ( or death )	Date of last adequate assessment of response 	Censored
New anticancer treatment started prior to documented disease progression 	Date of last adequate assessment of response  on or before starting new anti-cancer therapy	Censored
Death before first PD assessment (including death at baseline or prior to any adequate assessments)	Date of death	Event
Death between adequate assessment visits	Date of death	Event
Death or progression after more than one missed visit	Date of last adequate assessment of response  prior to missed assessments	Censored

 The earliest of (i) date of radiological assessment showing new intracranial or extracranial lesion (if progression is based on a new lesion); or (ii) date of radiological assessment showing unequivocal progression in intracranial or extracranial non target lesions, or (iii) date of last radiological assessment of measured intracranial and extracranial lesions (if progression is based on increase in sum of measured intracranial and extracranial lesions)

 An adequate assessment is defined as an assessment where the Investigator determined response is CR, PR, or SD.

 If PD and new anti-cancer therapy occur on the same day assume the progression was documented first; e.g., outcome is progression and the date is the date of the assessment of progression). If anti-cancer therapy is started prior to any adequate assessments, censoring date should be the date of first dose of study treatment.

PFS will be summarized using Kaplan-Meier estimates. Frequency of patients with PFS events will be presented and also separately by types of PFS event, i.e. progression or death. If there are a sufficient number of progressions or deaths, median PFS, first and third quartiles, and 95% CIs will be estimated using the Brookmeyer-Crowley method [Brookmeyer, 1982]. A figure and listing of progression-free survival time will also be provided.

PFS per independent reviewer-assessment will be summarized. A figure and listing of progression-free survival time per independent reviewer will also be provided.

#### Overall Survival in Cohorts A, B, C, and D

Overall Survival (OS) is defined as the interval of time (in months) between the date of first dose of study treatment and the date of death due to any cause. For subjects who do not die, time of death will be censored at the date of last contact. The date of death should be taken from that recorded on the Record of Death page. Death on study due to any cause will be included.

The date of last contact will be assigned to the latest date of: Exposure, randomization, death date, follow-up contact, or any actual assessment/procedure date in any data set. The following dates will NOT be included in the date of last contact calculations:

- Date of birth, date of initial cancer diagnosis, date when metastatic disease was first diagnosed, and date of disease staging at screening: These dates are prior to randomization.
- Date of withdrawal from the study: This date may not be associated with an actual subject visit.
- Date of protocol deviation: This date may not be associated with an actual assessment.
- Date of when dispensed investigational product bottles were returned: This date may not be associated with an actual subject visit. For example, a relative could return un-used drugs.
- Date when a sample was analyzed for BRAF mutation: This date is not associated with an actual subject visit.

If there are no post baseline data then the date of randomization will be the last contact date.

Survival will be summarized using the Kaplan-Meier for each cohort. In addition to the Kaplan-Meier estimates for median overall survival time, the first and third quartiles will be presented, along with approximate 95% CIs if there are a sufficient number of deaths.

A graph of survival curves and a listing of survival times will also be provided.

Analyses will be conducted at the time of the primary endpoint analysis as well as at the end of the study.

### 11.3. Other Efficacy Analyses

Summaries of comparisons between Investigator assessment and Independent Reviewer assessment of the Best intracranial, extracranial and overall Response for each subject will be provided overall by cohort. Also, a summary of comparison between investigator assessment and independent reviewer assessment of progression free survival times will be provided.

#### Concordance Analysis of Intracranial, Extracranial, and Overall Response Rates

An assessment of the concordance between Independent Reviewer assessment and Investigator Assessment of the Best Intracranial, Extracranial, and Overall Response for each subject will be provided overall across all cohorts. The calculation will be based on the percent agreement (the proportion of response outcomes that agree or match across both Independent Reviewer and Investigator Assessments):

Percent Agreement = (Number of matched responders + Number of matched non-responders) / total number of subjects assessed.

## 12. SAFETY ANALYSES

Unless otherwise specified, all the safety analyses will be based on the All Treated population as defined in Section 6 and summaries will include all events and assessments collected during the study. All the analyses will be performed by cohort.

The list of displays for safety analyses are shown in Section 14 of the RAP.

### 12.1. Extent of Exposure

Extent of exposure to dabrafenib and trametinib will be summarized separately.

The duration of exposure to study treatment in months (from first day to last day of treatment) will be summarized. Descriptive statistics including mean, median, standard deviation, minimum, and maximum will be calculated for time on study treatment. Moreover, time on study treatment will be categorized in different time period: <3 months, 3 months to 6 months, >6 months to 12 months and >12 months.

The subject's average daily dose, defined as the cumulative dose divided by the duration of exposure for each subject, will be summarized.

Dose reductions will be summarized by number of reductions and reasons for reductions for dabrafenib and trametinib separately. Dose interruptions will be summarized by number of interruptions, reasons for the interruptions, and interruption duration (days) for dabrafenib and trametinib separately. The mean, standard deviation, median, minimum value, and maximum value will be computed for the duration of interruptions as well as the number and percentage of the interruptions  $\leq 7$ , 8-14, 15-21 and >21 days.

All the dose reductions and dose interruptions will be listed separately.

## 12.2. Adverse Events

Adverse events (AEs) will be graded according to the CTCAE, Version 4.0. Adverse events will be coded to the preferred term (PT) level using the Medical Dictionary for Regulatory Affairs (MedDRA dictionary).

AE summaries will use the following algorithms for counting subjects:

- **Preferred term row:** Subjects experiencing the same AE preferred term several times with different grades will only be counted once with the maximum grade.
- **Any event row:** Each subject with at least one adverse event will be counted only once at the maximum grade no matter how many events they have.

An overview summary of AEs, including counts and percentages of subjects with any AE, AEs related to study treatment, AEs leading to permanent discontinuation of study treatment, AE leading to dose reductions, AEs leading to dose interruptions, SAEs, SAEs related to study treatment, fatal SAEs, and fatal SAEs related to study treatment will be produced. The same overview summary will be produced by sex and age groups (<65 and ≥ 65 years old)

The frequency and percentage of AEs (all grades) will be summarized and displayed in two ways: 1) in descending order of total incidence by PT only and 2) in descending order of total incidence by System Organ Classes (SOC) and PT. In the SOC row, the number of subjects with multiple events under the same system organ class will be counted once.

A summary of common (that is, that occurred in strictly 5% of the subjects or above) non-serious AEs will be provided. No rounding for the percentage will be used in terms of 5% threshold, e.g., event with 4.9% incidence rate should not be included in this table. The summary will be displayed by SOC and PT.

A summary of number and percentage of subjects with any adverse events by maximum grade will be produced. AEs will be sorted by Preferred term (PT) in descending order of total incidence.

The relationship between MedDRA SOC, PT, and Verbatim Text will be listed.

A separate summary for dabrafenib related, trametinib related, and dabrafenib and trametinib related AEs will be provided for study treatment-related AEs. A study treatment-related AE is defined as an AE for which the investigator classifies the relationship to study treatment as “Yes”. A worst case scenario approach will be taken to handle missing relatedness data, i.e. the summary table will include events with the relationship to study treatment as ‘Yes’ or missing. The summary table will be displayed in descending order of total incidence by PT only for each drug.

All AEs will be listed. Additionally, a listing of subject IDs for each individual AE will be produced.

### 12.3. Adverse Events of Special Interest

A comprehensive list of MedDRA terms based on clinical review will be used to identify each type of events. Changes to the MedDRA dictionary may occur between the start of the study and the time of reporting and/or emerging data from on-going studies may highlight additional adverse events of special interest, therefore the list of terms to be used for each event of interest and the specific events of interest will be based on the safety review team (SRT) agreements in place at the time of reporting.

An overview summary of AEs of special interest, including counts and percentages of subjects with any AE, AEs related to study treatment, AEs leading to permanent discontinuation of study treatment, AE leading to dose reductions, AEs leading to dose interruptions, SAEs, SAEs related to study treatment, fatal SAEs, and fatal SAEs related to study treatment will be produced.

The events of special interest include

- Skin related toxicities
- Ocular events
- Cardiac related events
- Hepatic disorders
- Pneumonitis/Interstitial lung disease
- Bleeding events
- Diarrhea
- Hypertension
- Edema
- Hypersensitivity
- Pyrexia
- Cutaneous squamous cell carcinoma including Keratoacanthoma
- Non-Cutaneous Treatment-Emergent Malignancies
- New primary melanoma
- Pre-renal and Intrinsic Renal Failure
- Uveitis
- Hyperglycemia
- Deep vein thrombosis/pulmonary embolism
- Pancreatitis
- Neutropenia

Summaries of the characteristics of each AE of special interest, including the number and percentage of subjects with these events will be provided for each separately. All summaries of AEs of special interest will use the number of subjects with the event as the denominator when calculating percentages. The summary of event characteristics will also be provided, including number of subjects with any event, number of events, number of subjects with any event that is serious, number of subjects with any event that is related to study treatment, the outcome of the event, maximum grade and the action taken for the event. The percentage will be calculated using the number of subjects with the event as the denominator. The worst case approach will be applied at subject level for the event outcome and maximum grade, i.e., a subject will only be counted once as the worst case from all the events experienced by the subject. For action taken in response to an event, subjects will be counted once under each action, e.g., if a subject has an event leading to both study treatment discontinuation and dose reduction, the subject will be counted once under both actions.

Summaries of onset for cutaneous squamous cell carcinoma including keratoacanthoma, and new primary melanomas (that is, AEs of special interest for which duration is not meaningful) will be produced. All other AEs of special interest will have summaries of the onset and duration produced.

In addition, subjects with each AE of special interest will be listed separately by AE of special interest.

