### **9.3.5. Key Elements of Analysis Plan**

Data will be listed and summarized according to the Novartis' reporting standards, where applicable. Complete details will be documented in the Reporting and Analysis Plan (RAP). Any deviations from, or additions to, the original analysis plan described in this protocol will be documented in the RAP and final study report.

As it is anticipated that accrual will be spread thinly across centres and summaries of data by centre would be unlikely to be informative, data from all participating centres will be pooled prior to analysis.

All data up to the time of study completion/withdrawal from the study will be included in analyses, regardless of duration of treatment.

The length of treatment for each subject will depend on the efficacy and toxicity of the treatment, so the duration of treatment and follow-up will vary among subjects. All available time-to-event data will be analyzed using appropriate statistical methods; subjects with shorter treatment and follow-up due to the natural history of their disease or medical necessities of the treatment of their disease will not be considered to have missing data. Consequently there will be no imputation for missing time-to-event data.

Demographic and baseline characteristics will be summarized according to current Novartis standards.

For the analysis of overall survival, the last date of known contact will be used for those subjects who have not died at the time of analysis; such subjects will be considered

censored.

For the analysis of PFS, if the subject received subsequent anti-cancer therapy prior to the date of documented progression or death, progression free-survival will be censored at the last adequate assessment (that is, the last assessment in which the visit level response is CR, PR, or SD) prior to the initiation of that anti-cancer therapy. Otherwise, if the subject does not have a documented date of progression or death, progression-free survival will be censored at the date of the last adequate assessment. Further details on rules for censoring will be provided in the RAP.

There will be no adjustments of the Type I error rate for multiplicity.

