##### **9.3.5.2.2. Adverse Events**

Adverse events (AEs) will be coded using the standard Medical Dictionary for Regulatory Activities (MedDRA) and grouped by system organ class. AEs will be graded by the investigator according to the NCI-CTCAE (version 4.0) [[NCI, 2009](#)].

Events will be summarized by frequency and proportion of total subjects, by system organ class and preferred term. Separate summaries will be given for all AEs, drug-related AEs, serious AEs and AEs leading to discontinuation of study treatment.

If the AE is listed in the NCI CTCAE (version 4.0) table, the maximum grade will be summarized.

Characteristics of the following AEs of special interest will be summarized separately: non-melanoma skin lesions, pyrexia, cardiac events, anaemia, and neutropenia. In particular, the rate of non-melanoma skin lesions will be calculated as the percentage of subjects with the appearance of any non-melanoma skin lesions after the start of treatment. Exact two-sided 95% confidence intervals for the rate of non-melanoma skin lesions in each arm will also be presented. Details will be given in the RAP.

The incidence of deaths and the primary cause of death will be summarized.

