### **6.4. Analysis Datasets**

Primary efficacy analyses will be based on investigator-assessed results in the ATS population. If independent review of efficacy is done, those analysis results will be secondary.

Safety analyses will use the ATS population.

The V600D/K/R population, defined above and identified in the study protocol as a population to be used to report on secondary efficacy endpoints by cohorts, will *not* be used. This change was made to accommodate the small sample size in Cohorts B-D (15 subjects per cohort). Analyses of subgroups of 15 subjects would not generally be meaningful and are not specified *a priori*.

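### SAP 12.3 divides special-interest AE percentages by the subjects who had the event, so the incidence row prints 100%; it also omits the protocol's non-melanoma skin lesion rate and exact CI without a recorded reason

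*SAP*

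**What the plan says.** SAP 12.3 sets out three kinds of AESI output.

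- An overview: "An overview summary of AEs of special interest, including counts and percentages of subjects with any AE, AEs related to study treatment", continuing through discontinuations, dose changes and serious and fatal events (Table 3.1600).
- A characteristics summary for each AESI. This includes the number and percentage of affected subjects, then seriousness, relatedness, outcome, maximum grade and action taken (Tables 3.1610 onwards).
- A summary of AESIs by maximum grade (Table 3.1090 in the display list).

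The denominator rule is general: "All summaries of AEs of special interest will use the number of subjects with the event as the denominator when calculating percentages". Two sentences later, for the event characteristics, the SAP says again: "The percentage will be calculated using the number of subjects with the event as the denominator".

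The default elsewhere is different. SAP section 12 opens with "Unless otherwise specified, all the safety analyses will be based on the All Treated population as defined in Section 6". Protocol 9.3.5.2.2 says of adverse events: "Events will be summarized by frequency and proportion of total subjects, by system organ class and preferred term".

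The same protocol section defines a non-melanoma skin lesion rate as a percentage of subjects and adds: "Exact two-sided 95% confidence intervals for the rate of non-melanoma skin lesions in each arm will also be presented". It leaves the details to the RAP. On departures from the plan, protocol 9.3.5 states: "Any deviations from, or additions to, the original analysis plan described in this protocol will be documented in the RAP and final study report".

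**The concern.** A percentage whose numerator and denominator are the same count carries no information. The affected-subjects row for every AESI would read 100% whether one subject or half the cohort was affected, and would have no value when nobody was.

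This matters most for grouped AESIs. Cardiac events, ocular events and skin-related toxicities each span several preferred terms, so no single preferred-term row in the general tables gives the proportion of subjects affected. The reader must rebuild the rate from the count and the cohort size. Cohort A has 75 planned subjects and the others about 15, so side-by-side reading depends on percentages of treated subjects. Safety of the combination is a secondary objective in all four cohorts.

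The skin lesion rate is a different kind of fault. It is the only adverse event rate for which the protocol specified an exact interval, and the SAP neither delivers it nor records its removal.

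**Working it through.** **1. The rule applied to the incidence row.** Let x be the number of subjects with the AESI and N the number treated in the cohort.

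- SAP 12.3 rule: percentage = 100 · x/x = 100% for x ≥ 1; 0/0, undefined, for x = 0.
- All-treated denominator: percentage = 100 · x/N.

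The planned cohort sizes (75 in A; 15 in B and D; up to 15 in C) come from protocol 4.1.1. The documents give no AESI counts for this trial, so the counts below are assumptions for illustration. Exact (Clopper-Pearson) 95% limits are the 0.025 quantile of Beta(x, N−x+1) and the 0.975 quantile of Beta(x+1, N−x). For x = 0 the lower limit is 0 and the upper limit is 1 − 0.025^(1/N).

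| N | x | SAP 12.3 prints | x/N | Exact 95% CI |
|---|---|---|---|---|
| 75 | 0 | undefined | 0.0% | 0 to 4.8% |
| 75 | 2 | 100% | 2.7% | 0.3 to 9.3% |
| 75 | 8 | 100% | 10.7% | 4.7 to 19.9% |
| 75 | 39 | 100% | 52.0% | 40.2 to 63.7% |
| 15 | 0 | undefined | 0.0% | 0 to 21.8% |
| 15 | 1 | 100% | 6.7% | 0.2 to 31.9% |
| 15 | 3 | 100% | 20.0% | 4.3 to 48.1% |

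The intervals show what a rate on N treated subjects can and cannot exclude. Neither document plans an interval for AESIs other than the skin lesion rate.

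**2. Convention check against the protocol's own background data.** Protocol 1.1.3.2 reports cutaneous squamous cell carcinoma in 3 subjects (2%) in Part B of the earlier combination study, with safety data on 125 subjects. 3/125 = 2.4%, which agrees with the printed 2%. The SAP 12.3 rule would print 3/3 = 100%.

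**3. How far the rule reaches.** The general sentence covers all AESI summaries, and a second sentence then repeats the rule for the characteristics summary alone. If only characteristics were meant, the general sentence would be redundant. Read literally, it also governs Tables 3.1600 and 3.1090, for which the SAP states no other denominator.

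**4. Tracing the skin lesion rate.**

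- AESI list in SAP 12.3: includes cutaneous squamous cell carcinoma with keratoacanthoma, and skin-related toxicities, but not non-melanoma skin lesions.
- Display list in SAP 14.1: no table for this rate. Tables 3.1616 and 3.1617 cover the narrower squamous cell/keratoacanthoma category, with no interval planned.
- Exact intervals in the SAP: planned only for response and disease control rates (section 11).
- SAP revision chronology: records the AESI list being updated for MedDRA 19.1, and exposure-adjusted AESI incidence rates being deleted. It does not mention the lesion rate or its interval.
- Contrast: SAP 6.4 names the protocol's V600D/K/R population, says it will not be used, and gives small cohort size as the reason.

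**The case against.** The best defence of the denominator is that the sentence sits in a paragraph about event characteristics. There, affected subjects are the right base for seriousness, outcome or action taken. The display mock-ups, held in a separate document, may use treated subjects for the incidence rows. This defence has some force: the intent may well have been narrower, and the reach to Tables 3.1600 and 3.1090 rests on a literal reading. But the wording is general, the rule is repeated for characteristics alone, and the affected-subjects percentage is promised in that same paragraph. Even on the narrowest reading, that row is x/x.

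It is also fair to say that the protocol's total-subjects wording concerns system organ class and preferred term, which Tables 3.1020 and 3.1030 deliver. The denominator fault is therefore mainly internal to the SAP, against its own all-treated default.

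Grade may look like an inconsistency, since affected subjects are accepted as the base within the characteristics summary but not for Table 3.1090. The two displays answer different questions. The first describes severity among those affected. The second is the AESI counterpart of the general maximum-grade table (3.1070), which follows the all-treated default.

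The practical loss is limited. Counts, listings and cohort sizes are reported, single-concept AESIs such as pyrexia are largely covered by preferred term, and no test or decision rule uses these percentages.

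On the lesion rate, SAP 12.3 says the AESI list will follow safety review team agreements, and the MedDRA update is logged. These can explain a changed list of terms but not the loss of a defined rate and its interval. One revision entry (item 8) has no visible text, and the terms behind skin-related toxicities are not shown, so the point is confined to what can be read.

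**Conclusion.** Both parts hold on the visible text. As written, SAP 12.3 makes the any-event percentage for each AESI 100% whenever at least one subject is affected, and undefined otherwise. True rates as far apart as 2.7% and 52.0% of 75 subjects would look identical. That result is arithmetic and does not depend on the assumed counts, which only illustrate its size. The extension to the overview and maximum-grade tables depends on reading the rule literally.

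The protocol's non-melanoma skin lesion rate with exact 95% interval is not planned in the SAP, and no removal is recorded, contrary to protocol 9.3.5. The primary endpoint is unaffected. This should be corrected because the planned AESI incidence percentages are uninformative and a protocol commitment lapses without explanation.

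**What to change.** In SAP 12.3:

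- Use all treated subjects in the cohort as the denominator for the any-event row of each AESI summary, the AESI overview (Table 3.1600) and the AESI maximum-grade table (Table 3.1090).
- Keep affected subjects as the denominator only for the characteristics rows (serious, related, outcome, grade, action taken), and label those rows as percentages of affected subjects.
- Add the non-melanoma skin lesion rate by cohort with its exact two-sided 95% interval, or state that it has been removed and why.

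The cost is one or two sentences of SAP text, a programming denominator, and either one display from data already collected or one sentence of justification.
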